11. STATISTICAL CONSIDERATIONS

11.1. Statistical Design and Data Analysis

Clinical diagnosis is based on 1) histopathology of biopsy/surgical specimen or 2) surveillance by CT scans for a period of 2 years to confirm that there is no growth of the nodule. Meta-analysis shows that ¹⁸F-FDG has a sensitivity and specificity of 89% and 75% respectively (16). We hypothesize that ¹⁸F-FSPG is more specific. With an expected 90% specificity for diagnosis with ¹⁸F-FSPG, a sample size of 60 will have 90% power at an alpha-level of 0.05 to demonstrate a significant increase in specificity from a fixed value of 75%.

Integrated predictions models:

Our biomarker discovery and validation will use samples from 930 patients in the intended use population collected prior to diagnosis; and subsample from all available cancer and non-cancer patients. Through our experience with the NCI Early Detection Research Network (EDRN), we have a detailed plan for biomarker discovery and validation, which is briefly summarized here.

¹⁸F-FSPG PET/CT and Integrated Biomarkers for Early Lung Cancer Detection in Patients with Indeterminate Pulmonary Nodules

Identification of candidate genes from nasal total RNA-seq data: We will initially select 20 to 40 candidate genes that significantly discriminate between cases (n = 100) and controls (n = 100). We will prioritize candidates to: 1) represent cancer-associated gene co-expression patterns, 2) genes whose expression is independent of clinical factors, and genes in significantly enriched functional categories.

Using single cell nasal RNA-seq to refine the nasal gene expression biomarker assay: We hypothesize that a subset of airway cells harbor lung-cancer associated gene expression differences (or that the distribution of cell types might distinguish the airway of cancer patients). We will perform scRNA-seq on cells collected prospectively from 200 patients (n = 100 each cases and controls). We will identify cell subpopulations using Celda and test for cell type-specific alterations associated with subtype, prognosis or disease activity using a strategy similar to that used for bulk RNA-seq data. Additionally, we will test for differences in cell population frequency associated with prognosis or disease activity; and also determine which cell subpopulations express the prognosis and disease activity associated genes identified in the bulk RNA-seq to understand the cellular architecture of these disease signatures. For biomarker development, we will interrogate the cellular architecture of the expression of the nasal biomarker genes. If biomarker gene expression localizes to specific cells, we would subsequently explore whether enriching for these cells improves biomarker performance. Alternatively, if the frequency of a nasal cell type differs in patients with lung cancer, we would explore whether quantifying this cell-type's frequency could serve as a lung cancer biomarker.

Identification of CT features: Similar to the gene expression analysis, our initial goal is to identify 5 to 10 candidate semantic or quantitative imaging features that optimally discriminate cases and controls. We will centrally process thin-section CT images resulting in a high-dimensional dataset of image features based on CAD detection and nodule segmentation, and quantitative feature extraction. Semantic analysis of CT scans will be conducted by thoracic imagers using an illustrated lexicon to maximize inter-reader agreement. A convolutional neural network (CNN) will derive synthetic quantitative measures predictive of cancer status via cross validation. The most cancer-discriminating quantitative and semantic features will be selected for downstream analysis.

Data Integration: Using a new set of 150 patients (75 cases and 75 controls), we will subset candidate genes and imaging features based on whether they improve (significantly higher ROC curve AUC) clinical lung cancer risk models with the goal of picking no more than 10 genes and 5 imaging features, and prioritizing genes least correlated with imaging features or the ctDNA biomarker. We will next use data from 380 new patients (n = 190 each cases and controls) to train and "lock down" models prior to validation. Model building will use a logistic regression framework (incorporating LASSO and ridge regression) and cross-validation. We will build models stepwise from clinical-variable-only models by adding additional biomarker datatypes (gene expression, imaging, and / or the ctDNA biomarker).

Cross validation will determine the gain in diagnostic performance from each additional datatype, and combinations that do not improve performance will be eliminated. These locked down models will be validated in the remaining samples (n = 200). The primary endpoint will be calculated after every patient has either completed two years of follow up, been diagnosed positive, or died, whichever comes first. The primary endpoint for validation of this prediction model will be replication of improved performance. Exploratory

¹⁸F-FSPG PET/CT and Integrated Biomarkers for Early Lung Cancer Detection in Patients with Indeterminate Pulmonary Nodules

endpoints will determine the range of pre-test probabilities for which the models have potential clinical utility.

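### The two single-cell tests name prognosis, subtype and disease activity as factors, so the cancer-versus-benign test that the hypothesis calls for is only implied

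*Combined protocol and SAP*

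**What the plan says.** The single-cell paragraph of section 11.1 opens with a cancer hypothesis: "We hypothesize that a subset of airway cells harbor lung-cancer associated gene expression differences". As an alternative, it suggests that the mix of cell types may differ in patients with cancer. The sample is 200 patients, 100 cases and 100 controls. Section 2.4 gives the same purpose for this work, namely where in the nasal epithelium cancer-associated expression sits.

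Two tests follow. The expression test is for "cell type-specific alterations associated with subtype, prognosis or disease activity", with a strategy said to resemble the one for the bulk data. The second will "test for differences in cell population frequency associated with prognosis or disease activity". A third task is to find which cell populations express "the prognosis and disease activity associated genes identified in the bulk RNA-seq".

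The bulk step, described just before in section 11.1, selects "20 to 40 candidate genes that significantly discriminate between cases (n = 100) and controls (n = 100". Section 11.2 sizes the discovery step on the same contrast: 100 cases and 100 controls, 80% power for an effect size of 0.52, false discovery rate 10%, 5% of markers differentially expressed. It gives no power statement for the single-cell step.

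The single-cell paragraph ends on biomarker use: "For biomarker development, we will interrogate the cellular architecture of the expression of the nasal biomarker genes". Two conditional sentences follow. One covers enriching for particular cells if the biomarker genes localise to them. The other covers using a cell type's frequency as a biomarker if that frequency differs in lung cancer patients.

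**The concern.** The hypothesis and the sample are about cancer versus benign disease, but the factors in the two test sentences are not. The gene list to be mapped is attributed to a step that is not described as producing it. The named factors also lack definitions: the study's clinical outcome (sections 2.6 and 11.1) is cancer or benign disease, from histopathology or two years of CT surveillance. Death is mentioned only as one of the events that fix when the endpoint is calculated.

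An analyst who follows the text must either supply the case/control contrast unprompted or work within the cases. The first leaves a choice among cancer status, subtype, prognosis and activity in high-dimensional data. The second discards half the sample and does not address the stated hypothesis.

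**Working it through.** The point is textual, so the statements are set side by side first. All are in section 11.1.

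| Element | Factor or content named |
|---|---|
| Hypothesis | Lung-cancer-associated expression, or cell mix in cancer patients |
| Sample | 100 cases, 100 controls |
| Expression test | Subtype, prognosis, disease activity |
| Frequency test | Prognosis, disease activity |
| Genes taken from the bulk step | Prognosis and disease-activity genes |
| Genes the bulk step yields | 20 to 40 genes separating cases from controls |

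The first two rows and the last agree with each other. The three between them do not fit. Case/control status appears in neither test sentence.

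**Reproducing the plan's own figure.** The only related figure is the 80% power of bulk discovery in section 11.2. With π = 0.05 (share of markers differentially expressed), power 0.80 and false discovery rate (FDR) 0.10:

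FDR = (1 − π)α / [(1 − π)α + π × power]

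α = 0.05 × 0.80 × 0.10 / (0.90 × 0.95) = 0.00468 per marker.

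Power for two groups of 100 at effect 0.52 (normal approximation, two-sided) is Φ(0.52/√(2/100) − z at 1 − α/2) = 80.2%. This matches the stated 80%. A noncentral t calculation gives 79.1%. A one-sided test would give 86.0%, so the plan's figure appears to be two-sided, although section 11.2 does not say so. The reproduced figure belongs to the case/control contrast.

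**Illustration for the single-cell step.** Assume the same per-marker α and 80% power, applied to one summary value per patient. The detectable effect in SD units is (z at 1 − α/2 + z at 0.80) × √(1/n₁ + 1/n₂). Subtype and prognosis contrasts can be formed only among the 100 cases. The documents give no split, so a range is shown.

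| Contrast | Detectable effect (SD) | Power at 0.52 |
|---|---|---|
| 100 cases vs 100 controls | 0.52 | 80% |
| Within cases, 50/50 | 0.73 | 41% |
| Within cases, 70/30 | 0.80 | 33% |
| Within cases, 80/20 | 0.92 | 23% |

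**The case against.** The strongest reply is that the cancer contrast is clearly intended. The sample is half cases and half controls, and the strategy is said to resemble the bulk one, which is case versus control. The closing sentences look at the nasal biomarker genes at cell level and anticipate a frequency difference in lung cancer patients. Section 11.1 also says that the detailed discovery plan is only summarised there. In addition, histopathology is one route to diagnosis, so a subtype comparison among cases is feasible, and an undefined disease activity might loosely include cancer status.

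Much of this stands. A reader might infer from the two test sentences that the single-cell step does not address cancer versus benign at all, or that its tests cannot be run. The documents support neither reading, for the reasons just given.

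The reply does not supply the missing specification. The closing sentences name no test. The one on cell frequency depends on a difference in lung cancer patients, while the frequency test actually stated is against prognosis or disease activity. The reference to a similar strategy describes method and is attached to the other factors. The reference to prognosis genes from the bulk step stays unsupported, because that step is described as selecting on case/control status only.

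**Conclusion.** The point holds as an inconsistency of specification. Both explicit single-cell tests name factors other than cancer versus benign status, and the genes they draw on do not match the output described for the bulk step. Two of the named factors, prognosis and disease activity, are undefined, and cancer subtype and prognosis have no counterpart in the 100 benign controls. The test that the hypothesis and the 100/100 sample call for is implied only.

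The detectable effects are an illustration and the conclusion does not rest on them. They assume that the bulk error control carries over to patient-level single-cell summaries, and the within-case splits are assumed. On that basis a within-case contrast needs an effect of 0.73 to 0.92 SD, against 0.52 for the full sample.

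The consequence is limited. Single-cell output is not among the data types listed for the integrated models in section 11.1. Neither the primary specificity outcome (section 10.1) nor the comparison of C statistics (section 10.2) is calculated from these tests. This is a minor correction, worth making before the single-cell data are analysed.

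**What to change.** In the single-cell paragraph of section 11.1:

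- Name cancer versus benign diagnosis as the tested factor in both the expression test and the cell-frequency test.
- Replace the reference to prognosis and disease-activity genes with the case/control candidate genes from the bulk step.
- Either define subtype, prognosis and disease activity, including how and when each is measured, and list them as exploratory analyses among cases, or delete them.

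The cost is wording only. No new samples or measurements are needed for the main contrast, which keeps all 100 versus 100 patients. Retaining prognosis or disease activity would require a definition and a data source, which the documents do not now give. Covariate adjustment of these tests is a separate choice that this point does not settle.

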11.2. Sample Size

Primary outcome: To compare 18F-FSPG PET/CT imaging with 18F-FDG PET/CT imaging for indeterminate lung nodules we will evaluate 120 patients. We estimate that approximately 60 of the patients will be diagnosed with lung cancer after complete diagnostic work-up and ~60 will not have lung cancer. Meta-analysis shows that 18F-FDG has a sensitivity and specificity of 89% and 75% respectively (16). We hypothesize that 18F-FSPG is more specific. With an expected 90% specificity for diagnosis with 18F-FSPG, a sample size of 60 will have 90% power at an alpha-level of 0.05 to demonstrate a significant increase in specificity from a fixed value of 75%.

Secondary outcome: In total the SU2C consortium cohort will be comprised of 930 study participants. Our Stanford group will contribute 120 (60 cases and 60 controls) to the larger sample set. Breakdown of the 930 patients are as follows. For the discovery step, sample size of 100 cases and 100 controls provides 80% power to detect RNA markers with effect sizes of at least 0.52 assuming that we will control the false discovery rate at 10% and 5% of markers are differentially expressed. For the refinement step, 75 cases and 75 controls provides 81% power to detect markers with a ROC AUC of at least 0.63 assuming an alpha level of 0.05. No correction for the multiple hypothesis testing is planned as we will re-evaluate top candidates. The sample size of 190 of each group for model building will support the following:

1. This sample size will be sufficient to include approximately 12 to 20 variables overall between clinical, imaging, ctDNA and gene expression markers based on conventional rules of thumb of 10 to 15 subjects per group per variable;
2. This will allow us to estimate the AUC for each model with a precision of approximately 4.5% (95% CI);
3. Provide 80% power for detecting delta AUCs between models of 0.06 assuming model correlation of 0.6.

For the model testing, 100 subjects in each group will provide AUC precision of ± 0.06 (and a precision of between 0.06 and 0.08 for the sensitivity and specificity), as well as a 80% power to detect differences in AUCs between models of 0.09. IRBs at the other sites have approved the collection of biospecimens and use of clinical / imaging data for this model development and validation work.

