10.2. Secondary Outcome Measure (ClinicalTrials.gov)

The secondary outcome is improved performance of an integrated prediction model to discriminate between benign and malignant lung nodules, compared with a clinical prediction model.

Outcome Title: Improved prediction model for lung nodules

Outcome Description: Improved performance is defined as a $p < 0.05$ increase in the C statistic determined using DeLong's test for correlated ROC curves.

Timeframe: Up to 5 years.

Safety Issue: No.

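### The 81% power for the refinement step belongs to a marker's own AUC (0.63 against 0.50), not to the added-value rule that decides which candidates are kept

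*Combined protocol and SAP*

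**What the plan says.** Section 11.2 (Sample Size, secondary outcome) justifies the refinement sample this way: "For the refinement step, 75 cases and 75 controls provides 81% power to detect markers with a ROC AUC of at least 0.63", at an alpha of 0.05. It gives no clinical-model AUC, AUC difference or correlation for this step. On multiplicity it says: "No correction for the multiple hypothesis testing is planned as we will re-evaluate top candidates".

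Section 11.1 (Data Integration) gives the selection rule for the same 150 patients: "we will subset candidate genes and imaging features based on whether they improve (significantly higher ROC curve AUC) clinical lung cancer risk models". The aim is a shortlist of at most 10 genes and 5 imaging features.

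For the two later steps, section 11.2 does state power as an AUC difference. With 190 per group it is "Provide 80% power for detecting delta AUCs between models of 0.06 assuming model correlation of 0.6". With 100 per group it is "80% power to detect differences in AUCs between models of 0.09".

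The only test for comparing AUCs that the plan names is in section 10.2, for the secondary outcome: "increase in the C statistic determined using DeLong's test for correlated ROC curves". Section 11.1 also says of its own text that "we have a detailed plan for biomarker discovery and validation, which is briefly summarized here".

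**The concern.** Detecting that a marker discriminates better than chance is one question. Showing that it raises the AUC of a model that already discriminates is another, and usually a much harder one with the same patients. Section 11.2 powers the first, and section 11.1 selects on the second.

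This step decides which of the 20 to 40 candidate genes and 5 to 10 imaging features reach model building, and section 11.1 describes no way back for a candidate that is dropped. A reader of section 11.2 would expect about 8 of every 10 markers at the AUC 0.63 floor to survive. If the added-value rule has far less power, useful weak markers, mainly single genes, are lost without the plan having said so.

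**Working it through.** **Inputs.** From section 11.2: 75 per group, marker AUC 0.63, alpha 0.05. Sidedness is not stated; two-sided is used because it reproduces the plan's figure. No clinical AUC is given for this step. Section 2.5 reports 0.76 for a clinical model (read here as an AUC), so 0.65 to 0.80 is assumed. Independence of marker and clinical score is also assumed. It is in line with the preference in section 11.1 for "genes whose expression is independent of clinical factors".

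**Step 1: the plan's own figure.** Hanley-McNeil variance with n = 75 per group:

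Var = [A(1−A) + (n−1)(U−A²) + (n−1)(V−A²)] / n², with U = A/(2−A) and V = 2A²/(1+A).

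- A = 0.50: [0.25 + 74×0.0833 + 74×0.0833]/5625 = 0.002237, SE 0.0473.
- A = 0.63: [0.2331 + 74×0.0630 + 74×0.0901]/5625 = 0.002055, SE 0.0453.
- Power with the null SE for the cut-off: Φ[(0.13 − 1.96×0.0473)/0.0453] = Φ(0.823) = 79.5%.
- Power with the alternative SE only: Φ(0.13/0.0453 − 1.96) = Φ(0.908) = 81.8%.
- One-sided, the same two calculations give 87.5% and 88.9%, which do not match.

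The text does not print the null of 0.50. It is inferred because it reproduces the 81%.

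**Step 2: the gain such a marker adds.** In the binormal model with unit variances, d = √2·Φ⁻¹(0.63) = 0.469 for the marker and D = √2·Φ⁻¹(clinical AUC). The best combined AUC is Φ(√(D² + d²)/√2). At clinical AUC 0.76, D = 0.999, √(0.998 + 0.220) = 1.104, and Φ(0.780) = 0.782, a gain of 0.022.

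**Step 3: power of the added-value rule, candidates tested singly.** Simulation with 4,000 data sets per setting compared the clinical score with the combined score by DeLong's test (z > 1.96). Weights were either fitted by logistic regression in the same sample or set to the true optimum (known).

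| Clinical AUC | Combined AUC | Gain | Correlation of scores | Mean SE of gain | Power, fitted | Power, known |
|---|---|---|---|---|---|---|
| 0.65 | 0.694 | 0.044 | 0.76 | 0.032 | 18% | 26% |
| 0.70 | 0.733 | 0.033 | 0.85 | 0.025 | 15% | 24% |
| 0.76 | 0.782 | 0.022 | 0.91 | 0.019 | 11% | 23% |
| 0.80 | 0.817 | 0.017 | 0.93 | 0.015 | 9% | 20% |

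Hand check at 0.76: Φ(0.0224/0.019 − 1.96) = Φ(−0.78) = 22%. Independent repeats gave 8% to 22% fitted and 19% to 31% known. With 10-fold cross-validated scores, power was 3% or less from clinical AUC 0.70 upward. DeLong's test is very conservative for nested models: at clinical AUC 0.76 with fitted weights, a null marker passed in 0.1% of sets.

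Retention per 10 floor candidates at clinical AUC 0.76 is 10×0.11 = 1.1 to 10×0.225 = 2.3, against 10×0.81 = 8.1.

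**Step 4: how far the result moves** (clinical AUC 0.76, fitted/known).

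- Stronger single marker: AUC 0.66, 24/33%; 0.70, 51/49%; 0.72, 67/61%; 0.74 (gain 0.070), 80/69%; 0.76 (gain 0.081), 90/79%. About 80% power therefore needs a gain of roughly 0.07 to 0.08.
- Joint test of independent AUC-0.63 markers: two, 43/42%; three, 76/61%; five, 97/82%. The fitted joint figures are in-sample and optimistic.
- Marker-clinical correlation of +0.2, +0.1, −0.1, −0.2: fitted 2, 5, 23, 42%; known 10, 15, 32, 44%.

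**The case against.** The sentence in section 11.2 can be read literally as stand-alone detection, and on that reading the 81% is correct arithmetic. The 9% to 26% rests on choices the plan does not make: DeLong's test at this step, one candidate at a time, two-sided testing, independence and an assumed clinical AUC. The rule asks for a higher AUC, which is directional. The headline case is the weakest marker allowed, while the candidates will have been chosen as top discriminators. The shortlist is capped and followed by retraining in 380 new patients, and no loss to the secondary outcome has been shown. The detailed plan behind this summary may settle the test.

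Much of this limits how firmly the size can be stated, and it stands to that extent. Joint testing, or markers well above 0.63, could bring power near or above 80%. Section 2.5 reports a combined semantic-imaging gain of 0.89 − 0.76 = 0.13, so imaging features taken together are less exposed. The effect on the final model is unknown.

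It does not remove the mismatch. One-sided testing of a single floor marker still gives only about 20% to 39%, and the most favourable correlation examined gives 44%. The later steps show that section 11.2 reports AUC-difference power where models are compared; only this step lacks it. Nor would the cap of 10 genes explain the loss: if all 20 to 40 genes sat at the floor, between 20×0.11 = 2.2 and 40×0.225 = 9.0 would pass.

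**Conclusion.** The concern holds. The 81% is the power to show that a single marker's AUC of 0.63 exceeds 0.50, and it is printed as support for a step whose rule is improvement over a clinical model.

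The size of the shortfall is conditional. For a single independent AUC-0.63 marker tested by DeLong, two-sided, power is about 9% to 26% over clinical AUC 0.65 to 0.80, and 11% to 23% at 0.76. Over a wider clinical AUC range of 0.60 to 0.89, the same setting gave about 3% to 29% before cross-validation. The plan's silence on the test and on single or joint testing is part of the problem, because power runs from about 10% to above 80% depending on that choice.

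The primary specificity analysis, the validation in the 200 patients and the ctDNA biomarker, which does not pass through this filter, are not affected.

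**What to change.** In section 11.2, label the 81% as power for a marker alone against AUC 0.50. Beside it, give the power of the added-value rule at 75 per group as a range, stating the clinical AUC, the marker-clinical correlation, and single or joint testing. The figures for 190 and 100 per group should not simply be scaled down: the scores compared here correlate 0.76 to 0.93, above the 0.6 assumed for the 0.06 difference.

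In section 11.1, name the test used at this step and say whether candidates are tested singly or jointly.

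One option, not required, is to screen single candidates with a likelihood-ratio test for adding the marker to the clinical logistic model, keeping DeLong's test for the locked models in the independent 200. Its power at 75 per group is about 69% to 78% for an independent AUC-0.63 marker, but about 33% at correlation 0.2 and clinical AUC 0.76. It tests added association rather than AUC gain, and about 5% of null candidates would pass to the penalised-regression stage.

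The cost is wording in two sections, agreement with the consortium's analysis group, and a modification through the IRB and SRC under section 9.2. Patients, data and software stay the same.
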